### **5.5 Medical Management and Safety Reporting**

Medical management will be according to the standard of care at each treating site and is not part of this research protocol. The investigator performing the submaximal exercise test will not be involved in the anaesthetic or surgical management for the patient's procedure. If, either when interviewing the patient or during the submaximal exercise test, the investigator has concerns about the peri-operative fitness of the patient, the clinical team will be informed. Aside from this, the clinical team will not be aware of the HRR test results, or pre-operative risk scores unless performed separately by the attending anaesthetist as per their usual care.

The submaximal exercise test will be terminated early if the patient demonstrates chest pain, intolerable dyspnoea, dizziness etc as per the ATS statement on the six minute walk test (6MWT). The exercise test will be performed in clinical areas, all of which are equipped with oxygen points and cardiac arrest trolleys, with clinical staff presence. All investigators will be trained in basic life support.

Tropionins and NT-proBNP will be blinded to the clinical teams. Blood tests will be linked-anonymised and analysed at the local NHS laboratory. They will be processed in real time and screened by the team for grossly abnormal results. If abnormal results are identified, the study team will discuss the result with the patient and arrange further medical follow-up if required.

## **5.6 Covid-19 Considerations**

We expect the Covid-19 pandemic will be abating by August 2021 when data collection is planned to start. However, there may still be potential for ongoing effects of the pandemic to affect the deliverability and validity of this study.

### **5.6.1 Deliverability**

The NIHR have published guidance concerning commencement of non-Covid research. This study has been designed with the NIHR framework in mind particularly concerning viability, capacity and safety. Locally this study has been risk assessed at level 3a (lowest risk): where patient attend hospital for clinically required interventions and follow-up is done remotely.

At present, all four centres' infection control policy requires the wearing of a surgical face-mask when in the hospital, unless there is a medical exemption. Therefore, all patients and investigators will wear face-masks for the duration of interview and exercise test, unless exempt. The wearing of a surgical face mask may affect heart rate, however as this measure is likely to be in place for the foreseeable future it aids to the generalisability of the study moving forward. This will not affect the scientific validity of the test as we are looking at HRR relative to resting and submaximal heart rate. Submaximal exercise testing does not fulfil the criteria of aerosol-generating procedure (private correspondence, Health Protection Scotland) and therefore no further infection control measures need to be taken apart from ongoing good infection control hygiene and the above.

### **5.6.2 Scientific validity**

Evidence continues to emerge on the multi-system effects of Covid-19 disease, particularly in regards to the increasing prevalence of "Long-Covid". It is plausible that recent Covid-19 infection, or development of "Long-Covid" syndrome after infection could be a confounder in this study. To mitigate against confounding, previous Covid-19 infection will be specifically investigated at patient interview with data recorded on date and severity of infection, along with co-morbidity relating to "Long-Covid".

## **6. Data Management**

### **6.1 Data collection**

Patient data will be collected locally via case report forms (CRFs) by one of the investigators or an appropriately trained research nurse. This data will be submitted electronically to a protected online database (Research Electronic Data Capture (REDCap), Vanderbilt University, Tennessee, USA) in linked-anonymised form with a unique alphanumeric study number allocated. The study will adhere to all data protection regulations. Patients' identities will be protected and their information held securely.

## **6.2 Data storage**

Anonymised patient data will be stored on password protected university and NHS hospital computers. A patient identifier list will be kept in a secure location within the Research Department of the hospital the patient was recruited from.

The data from each patient will be sent in an anonymised format to either NHS or University computers where analysis will be carried out. The research teams will not have access to the patient details from the other centres. If a patient needs to be contacted for any reason, contact will be made via the local recruitment team.

## **6.3 Archiving**

Study data will be archived for ten years after the completion of the trial. It will be filed and stored securely as per each local site's guidelines. At the end of ten years, the dataset will be destroyed to DoD 5220.22-M standards. All data will be held in accordance with General Data Protection Regulations (2018).

# **7. Statistical Considerations**

Our group has developed novel indices for measuring heart rate recovery including area under the curve and non-linear mixed effects modelling. This study is part of a higher degree programme (MD by research; [name]) which will encompass statistical methodology as an iterative process. The primary method of measuring HRR will be effort-corrected area under the curve (EC-AUC) but our other methods will also be examined. A formal statistical analysis plan will be written and agreed between the principal investigator (CH) and chief investigator (BS) prior to any data analysis.

All statistical analysis will be carried out using R-studio.

## **7.1 Power calculation**

A power calculation was performed based on the hypothesis that submaximal heart rate recovery will improve the AURROC for the prediction of post-operative myocardial injury from 0.5 (null hypothesis) to 0.7. Based on prior incidence of PMI of 24.5% after non-cardiac surgery in patients at higher risk of cardiovascular complications, 90 patients will be required, with a type 1 error of 0.05 and power of 80%. Adding an expected 5% dropout rate, a sample size of 95 patients will be recruited between the four recruiting centres. MedCalc V19.7.2 was used to calculate the sample size.

## **7.2 Primary Outcome**

Predictive ability of heart rate recovery of post-operative myocardial injury will be quantified by determination of area under the receiver operative characteristic curve.

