### **1.6 Previous HRR work**

Previous volunteer studies by our group have developed novel methods for HRR assessment utilising all the data contained within the HRR curve, including non-linear mixed-effects modelling and determination of the area under the curve (Figure 1), and have demonstrated their reproducibility following submaximal exercise across differing workloads and exercise modalities.

The exercise protocol for the submaximal test used in this investigation (detailed below) is based on these previous study findings. Specifically, this prior work reveals that in a healthy population, resting heart rate is approximately 40% predicted maximum heart rate (HRmax). Reproducibility across differing exercise modalities was demonstrated. Participants walked on a flat surface, performed a ramped protocol on an exercise bike, and repeatedly stepped on and off a low box. During the step test, participants reached a median (IQR) of 64%(62-72%) predicted HRmax. All of our previous work has examined HRR over a recovery time of six minutes. However, during the six minutes heart rate does not return to baseline, even when exercising at low levels (e.g. 20% predicted maximum power). In general, the heart rate curve plateaus after approximately four minutes after cessation of exercise (Figure 1).

The natural next step of our group's work therefore is the validation of effort-corrected submaximal HRR in a clinical population (Table 1).

[figure not shown]

Figure 1 Graphs demonstrating HRR curves after cessation of exercise. a) typical curve of fitter participant with high  $HRR_1$  and smaller AUC, incorporating lower resting HR. b) typical curve of less fit participant for comparison. Red dashed line = baseline HR. Yellow line = non-linear mixed-effects modelling curve from which rate constant can be obtained. AUC can be effort-corrected by dividing AUC by effort ratio (cessation HR/age-corrected maximal HR).

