### 1.7 Validation of clinical tests

In order for submaximal heart rate recovery to be used as a peri-operative risk measure, we need to demonstrate scientific validity. There are several types of validity which can be applied to a clinical test. Face validity is where the theoretical basis behind the measurement is scientifically sound and so taken at “face-value” represents what it purports to measure. Criterion validity is where the test is compared to a “gold-standard” criterion. Concurrent validity is where both measurements are taken concurrently and the test has the ability to distinguish between different groups of patients, for example, between patients at high or low risk of complications. Predictive validity is observed when the measurement identifies patients who develop a specific outcome. Construct validity is comparison of the measure against “constructs” used in place of the gold-standard. Table 1 details the types of validity and their application in the validation of submaximal heart rate recovery as a peri-operative risk stratification tool.

Table 1. Types of validity and how these will be applied to HRR measurement. Modified from Ferguson et al.

Validity Measure	Explanation	Example as applied to HRR
Criterion validity	Test corresponds to a gold standard measure	HRR is associated with cardiopulmonary exercise testing derived indices – anaerobic threshold (AT) and peak $VO_2$ ( $VO_{2\text{peak}}$ )
Concurrent validity	Test is able to distinguish between groups that theoretically it should be able to distinguish between	High risk patients as determined by CPET  : 
 
• AT <10ml/kg/min
 
• <math>VO_{2\text{peak}} < 20\text{ml/kg/min}</math>
 
• <math>VE/VCO_2</math> at AT >34
 

Predictive validity	Test is able to predict something it theoretically should be able to predict	Identifies patients with poor post-operative outcomes e.g. myocardial injury
Construct validity	Extent to which the test corresponds to other measurements that theoretically support the concept (or construct) being measured	Association observed between HRR and clinically used pre-operative risk predictors e.g. METs score, DASI, Clinical frailty score, Revised cardiac risk index, P-POSSUM and NT-ProBNP

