#### 5.3.1 **Baseline demographic data**

Case note review and routine pre-operative investigations:

- Age
- Sex
- Ethnicity
- Height and weight
- Operation
- Indication for operation
- Alcohol consumption (units/week)
- Smoking history (current and pack years; time since abstinence if applicable)
- Metabolic equivalents

- American Society of Anaesthesiology score
- Clinical Frailty Score
- Co-morbidity (including history of Covid-19 infection)
- Drug history, including medication taken on day of test
- Routine observations (blood pressure, oxygen saturations, respiratory rate)
- Pre-operative ECG finding
- Consultant Anaesthetist caring for the patient on the day of surgery's perception of peri-operative risk as per their routine risk assessment

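### Does recording test-day medication without a stated analytic use weaken the primary AUROC for heart rate recovery?

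*Combined protocol and SAP*

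**What the plan says.** Section 7.2 gives the whole primary analysis in one sentence: "Predictive ability of heart rate recovery of post-operative myocardial injury will be quantified by determination of area under the receiver operative characteristic curve". No covariate, stratum or sensitivity analysis is attached. The index test is fixed in section 7: "The primary method of measuring HRR will be effort-corrected area under the curve (EC-AUC"), with other methods also to be examined. The caption of Figure 1 (section 1.6) explains the correction: "AUC can be effort-corrected by dividing AUC by effort ratio (cessation HR/age-corrected maximal HR"). Section 5.4.2 computes maximal heart rate from age alone, as 208 - 0.7 × age.

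The baseline list in section 5.3.1 includes "Drug history, including medication taken on day of test". Neither section 7.2 nor section 7.3 mentions this item again. Section 7 says of the detailed analysis: "A formal statistical analysis plan will be written and agreed", with agreement to come before any data analysis.

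The aim in section 1.9 includes predictive validity, and section 1.7 says what that means: "Predictive validity is observed when the measurement identifies patients who develop a specific outcome".

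**The concern.** Asking specifically about medication on the test day suggests that the investigators thought it might affect the reading. The protocol also takes care over other influences on heart rate: section 4.2.1 justifies excluding pacemakers, section 5.4.2 asks patients not to speak, and section 5.6 discusses masks and Covid-19. Medication gets no such discussion. Masks are set aside in section 5.6.1 because "we are looking at HRR relative to resting and submaximal heart rate", and that reasoning would not obviously protect effort-corrected AUC (EC-AUC) from a drug that lowers resting heart rate, since dividing by the effort ratio leaves resting heart rate in the area.

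If users of such drugs had both different EC-AUC values and a different injury risk, some of the reported discrimination would reflect prescribing rather than fitness, and a reader could not tell how much, although the data had been collected.

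**Working it through.** **1. What the primary analysis has to answer.** The AUROC is the probability that a randomly chosen injured patient has a higher-risk reading than a randomly chosen uninjured one. Section 1.7 defines predictive validity as identifying those who develop the outcome, in patients as they present. A predictive claim of this kind needs no adjustment for the causes of the reading. Measure and question match.

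**2. The plan's own figure.** Section 7.1 gives AUROC 0.5 against 0.7, incidence 24.5%, type 1 error 0.05, power 80%, and 90 patients. With n₁ injured, n₂ uninjured, a = A/(2-A) and b = 2A²/(1+A), the Hanley-McNeil variance is

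var(A) = [A(1-A) + (n₁-1)(a-A²) + (n₂-1)(b-A²)] / (n₁n₂).

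For 22 + 68 = 90 the standard error is 0.0712 at A = 0.5 and 0.0685 at A = 0.7. Two-sided power is Φ[(0.20 - 1.96 × 0.0712)/0.0685] = Φ(0.88) = 81.1%. Dropout: 90/0.95 = 94.7, rounded up to 95. Both figures reproduce, and medication plays no part in them.

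**3. Would a drug move EC-AUC, and which way?** The documents do not say, so everything here is assumed: age 68, so HRmax = 208 - 0.7 × 68 = 160.4; resting rate 75, cessation rate 101; exponential return to rest with time constant 1.2 min over 5 min. Area from zero = 5 × rest + (cessation - rest) × 1.2 × (1 - e^(-5/1.2)); area from baseline drops the first term. Each is divided by cessation/160.4.

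| Case | From zero | From baseline |
|---|---|---|
| Rest 75, cessation 101 | 644.3 | 48.8 |
| Rest 65, cessation 101 | 583.7 (-9.4%) | 67.5 (+38%) |
| Rest 65, cessation 86 | 652.4 (+1.3%) | 46.3 (-5.1%) |

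The sign depends on the reference level and on whether cessation rate falls too. Over a range of assumed population spreads, the -9.4% case is -0.75 to -1.06 SD. On that scale +1.3% is about 0.10 to 0.15 SD (1.3/9.4 = 0.138, times 0.75 and 1.06). So shifts of 0.5-1.0 SD, used next, leave out near-null cases and are not a cautious choice.

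**4. How far could the pooled AUROC move?** Assume equal-variance normal readings, AUROC 0.70 within each drug group (separation m = √2 × Φ⁻¹(0.70) = 0.742) and a shift d in users. Let u₁ and u₀ be the share of users among injured and uninjured patients. Then

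pooled = [u₁u₀ + (1-u₁)(1-u₀)] × 0.70 + u₁(1-u₀) × Φ((m+d)/√2) + (1-u₁)u₀ × Φ((m-d)/√2).

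With 30% users and odds ratio 1.5, injury risk is 29.9% in users and 22.2% in non-users, so u₁ = 0.367 and u₀ = 0.278. At d = -0.75: 0.559 × 0.70 + 0.2645 × 0.498 + 0.176 × 0.854 = 0.674, a difference of -0.026. At d = +0.75 the last two probabilities swap, giving 0.705, or +0.005.

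Over 20-40% users, odds ratios 1.0-2.0 and shifts of 0.5-1.0 SD either way, the difference runs from -0.060 to +0.019. The simulated standard error of the pooled AUROC at n = 90 is 0.063-0.070. Setting m = 0, so that only drug use carries information, the pooled AUROC is 0.456-0.544.

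**5. Would an adjusted AUROC isolate the drug contribution?** At odds ratio 1.0 drug use says nothing about injury, yet pooled minus adjusted is still -0.013 to -0.020 for a 1 SD shift in either direction, because the shift only blurs the ranking. The contrast therefore mixes dilution with any drug-injury association. In simulation, the 95% interval for the difference excluded zero in 0.5-0.7% of runs with no shift, 9-17% at -0.75 SD and 3-4% at +0.75 SD.

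**The case for a change.** The strongest reply is that the protocol presents heart rate recovery as a marker of vagal tone and functional capacity (sections 1.3 to 1.5), so a reader will want to know whether the AUROC reflects fitness or prescriptions. The data are on the CRF, the extra analysis is a few lines, and choosing the drug list before seeing results guards against selective coding. Wider assumptions also give larger movements: with 20-50% users and risk ratios of 1.5-3, a within-group 0.70 could appear as about 0.60 to 0.76 pooled, and 0.10 is more than one standard error.

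It is true that medication has no stated analytic role and that a pooled AUROC cannot apportion its sources. But the same applies to smoking, alcohol, ethnicity and ECG findings in section 5.3.1; a baseline list is not a list of adjustments, and the detail belongs to the SAP that section 7 promises. The mask sentence in section 5.6.1 is about masks, and the protocol never uses it to dismiss drugs. Even under the wider assumptions, a marker with no discrimination within drug groups reaches at most about 0.59.

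Whether the area runs from zero or from baseline is a separate matter of definition. The caption's phrase "smaller AUC, incorporating lower resting HR" points to zero, and the figure itself or the source cited for EC-AUC may settle it. Neither was available here.

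**Conclusion.** The concern does not hold. Followed as written, the plan gives a valid estimate of what it sets out to estimate: how well EC-AUC, measured in patients as they present, ranks those who will have myocardial injury above those who will not. Missing adjustment for test-day medication does not bias that estimate.

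That any drug changes heart rate recovery, and by how much, is an assumption with no support in the documents; so are the prevalence of use and its association with injury. Within the main assumed range the difference is -0.060 to +0.019, below one standard error at n = 90, and drug use alone would not produce 0.70. A drug-adjusted AUROC would be descriptive, would not separate the two effects it mixes, and would leave the conclusion and the sample size of 90 (95 recruited) unchanged. Adding one is a matter of preference for the SAP authors.

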## **7.3 Secondary Outcomes**

Secondary outcomes such as post-operative complications, patient-reported outcome measures, clinical indicators and CPET substudy will be analysed using appropriate statistical methods.

Paired secondary outcomes will be assessed for normality. Comparison will be made using a paired t-test or Wilcoxon signed ranks test. ANOVA or Friedmann's test will be used to assess differences between variables repeated over time. Association will be sought between HRR and appropriate variables using Pearson correlation coefficient or Spearman's rank correlation coefficient as appropriate.

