## 1. **Background and rationale**

### 1.1 **Introduction**

There are approximately 1.5 million major operations performed in the UK annually, with the majority of these surgeries carrying an intermediate (1-5%) or high (>5%) mortality risk. The number of operations performed annually is increasing concurrent with an increase in population age and therefore the prevalence of co-morbidities. Despite this, surgical mortality is reducing. In 2017 all major NHS surgery was found to have a 30-day mortality of 1.1%. A planned sub-analysis of the ENIGMA-II study demonstrated that 15.7% of patients with increased peri-operative cardiovascular risk undergoing non-cardiac surgery developed a major post-operative complication. This was associated with a 1-year disability-free survival of 87.5% and a 1 year mortality of 7.4%. As well as increasing the risk of mortality and further morbidity, post-operative complications have been shown to cause detriment to an individual's quality of life. Post-operative complications also affect wider society by adding a financial burden on limited NHS resources, and reducing the ability of patients and their families to contribute towards the economy. One of the main ways to mitigate post-operative complications is via effective pre-operative risk stratification.

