#### **4.3 Withdrawals and exclusions**

A patient may request withdrawal from the study at any time without it affecting their clinical care. The patient will not have to give a reason for their decision to withdraw.

Participants will be made aware from the beginning of their participation in the study that they can freely withdraw (discontinue participation) from the study (or part of) at any time. The sample size calculation allows for participant withdrawal of approximately 5%, so it is not anticipated that it will be necessary to replace participants who withdraw. The situation will be monitored throughout the study by the Chief Investigator.

Types of withdrawal will be collected on a "Change of Status Form" defined as:

- The participant would like to withdraw from the study but is willing to be remotely followed up in accordance with the schedule of assessments (i.e. the participant has agreed that data from medical notes can be collected and used in the study analysis but they do not want to be contacted via telephone for questionnaires from that point onwards).
- The participant would like to withdraw from the study and is not willing to be followed up in any way for the purposes of the study and for no further data to be collected (i.e. only data collected prior to the withdrawal can be used in the study analysis).
- The participant wishes to withdraw completely from the study and all study follow up, and is not willing to have any of their data, including that already collected, to be used in any future analysis.

The details of withdrawal (date, reason and type of withdrawal) will be clearly documented in the source data and on the "Change of Status Form".

All patients will be consented pre-operatively, but can withdraw consent at any time. Patients undergoing some high risk procedures e.g. elective AAA repair may be admitted to Intensive Care post-operatively, and may be sedated for longer than one post-operative day. This will be explicitly clarified with the patient pre-operatively, and confirmed that troponin levels and post-operative complication data will still be collected and recorded if they are unconscious. However, the day 2 QoR-15 scale will not be performed. If sedation is required for longer, the

patient-centred secondary outcomes may not be completed but we envisage this will be a minority of patients. All other post-operative complication and clinical indicator data will be collected from notes reviews.

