#### **5.3.6 Post-operative questionnaires**

- QoR-15 at day 2.
- EQ-5D-5L at day 90 and 1 year.

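### ANOVA or Friedman's test on EQ-5D-5L discards observed scores when one of the three is missing; a mixed model would keep them, and a rule for death is needed

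*Combined protocol and SAP*

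**What the plan says.** Section 7.3 names three sets of methods. For measures taken repeatedly, "ANOVA or Friedmann's test will be used to assess differences between variables repeated over time". Paired outcomes go to a paired t-test or Wilcoxon signed ranks test. Association with HRR is assessed by a Pearson or Spearman coefficient. Beyond that, the choice of method for patient-reported outcomes is left open. The section names no analysis population and gives no rule for a missing questionnaire or for a patient who has died.

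The two questionnaires have different schedules. Section 5.3.6 sets "EQ-5D-5L at day 90 and 1 year", and section 5.3.3 and Table 2 add a pre-operative score, so EQ-5D-5L has three time points. QoR-15 has two: pre-operative and day 2. Section 12 says that the three-month and one-year questionnaires are done by telephone.

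Section 4.3 expects some of these data to be missing. For patients sedated beyond the first post-operative day it says: "However, the day 2 QoR-15 scale will not be performed". After longer sedation, other patient-centred outcomes may also be missing, which is expected in a minority. Participants may also stop telephone questionnaires while data from their notes are still collected.

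The opening of section 7 promises a formal SAP, to be agreed before any data analysis.

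**The concern.** Repeated-measures ANOVA and Friedman's test, as usually run, need a value at every time point. One missing EQ-5D-5L score therefore removes the whole patient from the comparison over time, including scores already collected. Death before 1 year is one route to a missing score. If patients with incomplete series tend to have had a worse course, the trajectory describes a healthier group than the one recruited.

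The plan does handle comparable problems elsewhere. Acute kidney injury has a fallback when urine output is not recorded (section 5.3.5 and Appendix 3), days alive and out of hospital reflects mortality, and length of stay is reported with and without in-hospital mortality. The questionnaires have no equivalent rule.

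**Working it through.** **The plan's own figure.** The only sample-size figure is for the primary outcome: "90 patients will be required, with a type 1 error of 0.05 and power of 80"%, for an AUROC moving "from 0.5 (null hypothesis) to 0.7", with an incidence of 24.5%. It can be reproduced with the Hanley-McNeil variance

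V(A) = [A(1 − A) + (n1 − 1)(A/(2 − A) − A²) + (n0 − 1)(2A²/(1 + A) − A²)] / (n1 × n0).

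- The ratio of negatives to positives is 0.755/0.245 = 3.08. With n1 = 22, n0 = 68.
- V(0.5) = 7.583/1496, so SE = 0.0712. V(0.7) = 7.021/1496, so SE = 0.0685.
- (0.2 − 1.96 × 0.0712)/0.0685 = 0.88, which gives power of 81.1% at 22 + 68 = 90.
- Dropout: 90/(1 − 0.05) = 94.7, rounded up to 95.

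The stated 90 and 95 are therefore sound (two-sided test). The 5% is an allowance on an endpoint complete by day 2. It was not derived for a year of questionnaires, and no figure is given for those.

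**What the named tests keep.** EQ-5D-5L scores used in the comparison over time, by pattern:

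| Pattern | Scores observed | Used by standard ANOVA or Friedman | Used by mixed model |
|---|---|---|---|
| All three obtained | 3 | 3 | 3 |
| Dies, or stops telephone contact, between day 90 and 1 year | 2 | 0 | 2 |
| Misses the day-90 call only | 2 | 0 | 2 |
| Dies before day 90 | 1 | 0 | 1 |

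**How many series might be incomplete (illustration).** Complete series = 95 × (1 − m) × (1 − w), where m is 1-year mortality and w is other loss. The documents give neither for this cohort. Two figures in section 1.1 serve as assumed anchors for m: 1.1% (30-day mortality, all major NHS surgery) and 7.4% (1-year mortality in a cited sub-analysis). The values of w are assumed.

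| m | w = 0% | 5% | 10% | 20% |
|---|---|---|---|---|
| 1.1% | 94.0 | 89.3 | 84.6 | 75.2 |
| 7.4% | 88.0 | 83.6 | 79.2 | 70.4 |

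**Possible effect on a mean (illustration).** If a share f of patients is missing and they are d SD worse than completers, the completer mean is too favourable by f × d. With f from 5% to 20% and d from 0.5 to 1.5 (all assumed), that is 0.05 × 0.5 = 0.025 SD to 0.20 × 1.5 = 0.30 SD. A mixed model would remove only the part explained by the scores and covariates that it uses.

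**Possible effect on a correlation (illustration).** This bears on the Pearson or Spearman analyses, not on ANOVA or Friedman. In a bivariate-normal simulation with a true correlation of 0.30 and 5% to 20% missing:

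- missing at random with respect to the score: 0.30;
- partly related to a poor score: 0.29 to 0.27;
- exactly the worst scores missing: 0.27 to 0.23.

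The standard error of such a correlation is about (1 − 0.30²)/√94 = 0.09, so the first two cases are hard to tell apart in this study.

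**The case against.** The strongest reply is that nothing has been fixed. Section 7.3 does not name EQ-5D-5L in the ANOVA and Friedman sentence, it leaves room for other methods, and a formal SAP is still to come. That stands as far as it goes: a reader might infer that the protocol prescribes a completers-only analysis, and it does not. That analysis is the default of the tests it names, combined with silence on missing data. But EQ-5D-5L is the questionnaire with three time points, and the tests named for such data are less suitable than an available alternative.

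Four further inferences go beyond the documents.

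- **That QoR-15 is affected in the same way.** It has two time points, so the paired-test and correlation sentences govern it.
- **That the ANOVA or Friedman rule weakens the HRR association.** That association is sought by Pearson or Spearman, which need only HRR and the score at the time point examined. A patient who dies in month 8 can still contribute a day-90 score.
- **That sedated patients are those recovering worst.** Section 4.3 links sedation to some high-risk procedures and has it discussed with the patient beforehand. It may reflect the operation.
- **That about 7 patients die, about 12 are dropped and the 1-year mean is wrong by 0.05 to 0.06.** These come from 95 × 0.074 = 7.0, 95 × (0.074 + 0.05) = 11.8, and 0.074 × 0.7 to 0.8 (assumed survivor scores). Section 1.1 reports "a 1 year mortality of 7.4"% directly after a 15.7% rate of major complications, and the figure may belong to those patients only; they alone would give 95 × 0.157 × 0.074 = 1.1 deaths. The 5% is a withdrawal allowance not tied to outcome. The 0.05 to 0.06 is the effect of scoring death as 0, not a bias that a mixed model would remove.

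Poor outcomes are also captured elsewhere: troponin and complications are collected in unconscious patients, and mortality and days alive and out of hospital are separate outcomes.

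**Conclusion.** The concern holds in a limited form and is minor. For EQ-5D-5L over time, the tests named in section 7.3 would, in standard form, discard observed scores from any patient with an incomplete series, and no rule covers death or missing questionnaires. For day-2 QoR-15, the gap is that missingness from sedation or death is foreseeable but has no stated reporting or analysis.

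No bias can be quantified from the documents. The 94 to 70 complete series, the 0.025 to 0.30 SD shift and the correlation figures all rest on assumed mortality, loss and severity, and serve only to show a range. The primary outcome and its sample size are unaffected.

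**What to change.** In the SAP, before any data analysis:

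1. Analyse EQ-5D-5L over time with a linear mixed model using every available score, with time (pre-operative, day 90, 1 year) as a categorical effect and within-patient correlation modelled. HRR can be added as a covariate.
2. Add a sensitivity analysis scoring death as 0. Label it as a different estimand and report it beside the observed-data result. State which EQ-5D-5L score is used, since 0 must have a meaning on that scale.
3. State the analysis population for each questionnaire, and report the number missing at each time point by reason: death, sedation, withdrawal, missed call.
4. For day-2 QoR-15, report the number missing because of sedation or death. Optionally add a Spearman analysis giving these patients the worst rank, with the caveat that sedation may reflect the procedure.

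The cost is SAP wording and slightly more analysis; recruitment and data collection do not change. The group already uses mixed-effects modelling for HRR curves (section 1.6). The drawbacks are that the mixed model relies on data being missing at random and treats scores after death as merely missing, and that the zero and worst-rank scores are conventions. This is why they sit beside the observed-data result and do not replace it.
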